STUDY NAME: CLINICAL EVALUATION OF SAFETY AND EFFICACY OF RADIO-FREQUENCY ASSISTED LIPOLYSIS (RFAL) OF BREAST ENVELOPE AND NIPPLE-AREOLAR COMPLEX (NAC) POSITION

Date:

August 2018

Identifiers: NCT03863834 Unique Protocol ID: D0607738

I N M O D E
aesthetic solutions

Clinical Evaluation of Safety and Efficacy of Radio-Frequency Assisted Lipolysis (RFAL) of Breast Envelope and Nipple-Areolar Complex (NAC) Position

Protocol No:
DO607738A

Rev. Date: August, 2018

SIRB ID: 6254

STUDY NAME: CLINICAL EVALUATION OF SAFETY AND EFFICACY OF RADIO-FREQUENCY ASSISTED LIPOLYSIS (RFAL) OF BREAST ENVELOPE AND NIPPLE-AREOLAR COMPLEX (NAC) POSITION

Date: August 2018

Protocol No: D0607738

Revision No.: B

Sponsor: InMode MD Ltd.

[name]
[name]
[name]
[name]
[contact]
[contact]

INMODE

aesthetic solutions

Clinical Evaluation of Safety and Efficacy of Radio-Frequency Assisted Lipolysis (RFAL) of Breast Envelope and Nipple-Areolar Complex (NAC) Position

Protocol No:
DO607738A

Rev. Date: August, 2018

SIRB ID: 6254

APPROVALS:

	Name	Title	Signature	Date
Written by:	[name]	CLINICAL MANAGER		
Edited by:	[name]	VP, RESEARCH AND COMPLIANCE		
Approved by:				

Revision Log:

Revision #	Date	Modification
A		First Release
B	8.8.18	

INMODE
aesthetic solutions

Clinical Evaluation of Safety and Efficacy of Radio-Frequency Assisted Lipolysis (RFAL) of Breast Envelope and Nipple-Areolar Complex (NAC) Position

Protocol No:
D0607738A

Rev. Date: August, 2018

SIRB ID: 6254

PROTOCOL SYNOPSIS

Study Title	CLINICAL EVALUATION OF SAFETY AND EFFICACY OF RADIO-FREQUENCY ASSISTED LIPOLYSIS (RFAL) OF BREAST ENVELOPE AND NIPPLE-AREOLAR COMPLEX (NAC) POSTION
Study Number	D0607738A
Principal Investigators	[name]
Study Design	This is a single center clinical study to determine the safety and efficacy of using Radiofrequency (RF) energy for minimally invasive breast lift procedure. Treatment areas will include breast area.
Study Sites / Country	[name] Maxwell Aesthetics [name]
Planned Study Duration	Study duration including recruitment will be up to 18 months.
Investigational Product	The InMode RF™ platform has been cleared by the United States Food and Drug Administration (FDA) (K151793) for use in dermatological and general surgical procedures for electrocoagulation and hemostasis.
Planned Sample Size	Up to 10 adult subjects
Subject Selection	Investigator will determine patient's eligibility to participate in the study according to inclusion/exclusion criteria.

INMODE
aesthetic solutions

Clinical Evaluation of Safety and Efficacy of Radio-Frequency Assisted Lipolysis (RFAL) of Breast Envelope and Nipple-Areolar Complex (NAC) Position

Protocol No:
DO607738A

Rev. Date: August, 2018

SIRB ID: 6254

Study Objectives	The purpose of this study is to evaluate the safety and efficacy of RFAL for the Breast Envelope and Nipple-Areolar Complex (NAC) Position as measured by the Vectra 3D circumferential imaging system (Canfield, NJ).
Main Eligibility Criteria	
Inclusion Criteria
 
• Informed consent agreement signed by the subject.• Healthy females 21 to 60 years of age.• Presence of grade I-III Breast Ptosis, mastopexy with history of breast augmentation, correction of asymmetry, mastopexy alone, mastopexy following implant removal and modest breast reduction in combination with or without lipoaspiration.• Post-menopausal or surgically sterilized or using a medically acceptable form of birth control at least 3 months prior to enrolment and during the entire course of the study (i.e., oral contraceptives, IUD, contraceptive implant, barrier methods with spermicide, or abstinence).• Willingness to follow the treatment and follow-up schedule and the post-treatment care.• All participants must have a recorded mammogram before the beginning of the study. 
Exclusion Criteria
 
• Pacemaker or internal defibrillator, or any other active electrical implant anywhere in the body.

INMODE
aesthetic solutions

Clinical Evaluation of Safety and Efficacy of Radio-Frequency Assisted Lipolysis (RFAL) of Breast Envelope and Nipple-Areolar Complex (NAC) Position

Protocol No:
DO607738A

Rev. Date: August, 2018

SIRB ID: 6254

- Permanent implant in the treated area such as metal plates and screws, silicone implants or an injected chemical substance.
- Current or history of skin cancer (remission of 5 years), or current condition of any other type of cancer, or pre-malignant moles.
- Severe concurrent conditions, such as cardiac disorders, epilepsy, uncontrolled hypertension, and liver or kidney diseases.
- History of bleeding coagulopathies or use of anticoagulants in the last 2 weeks.
- Impaired immune system due to immunosuppressive diseases such as AIDS and HIV or use of immunosuppressive medications.
- Poorly controlled endocrine disorders, such as diabetes or thyroid dysfunction.
- Any active condition in the treatment area, such as sores, psoriasis, eczema, and rash.
- History of skin disorders, keloids, abnormal wound healing, as well as very dry and fragile skin.
- Use of Isotretinoin (Accutane®) within 6 months prior to treatment.
- Significant systemic illness or occult systemic illness.
- Illness, infection or skin diseases localized in area of treatment.
- Other therapies or medication which may interfere with treatment.
- Breastfeeding, pregnant, or planning to become pregnant during the study.
- Allergy to lidocaine or other anaesthesia.

INMODE
aesthetic solutions

Clinical Evaluation of Safety and Efficacy of Radio-Frequency Assisted Lipolysis (RFAL) of Breast Envelope and Nipple-Areolar Complex (NAC) Position

Protocol No:
DO607738A

Rev. Date: August, 2018

SIRB ID: 6254

	
• Recent surgery in treatment area within the past 6 months.• Participation in a study of another device or drug within 3 months prior to enrolment or during this study.• As per the Investigator's discretion, any physical or mental condition which might make it unsafe for the patient to participate in this study.• As per the practitioner's discretion, refrain from treating any condition that might make it unsafe for the patient.
Risk to the Subject	
Risks involved with study participation, include:
 
1. Pain2. Excessive swelling (Edema)3. Excessive skin redness (Erythema)4. Bleeding5. Bruising6. Burn7. Blistering8. Crusting9. Scarring10. Skin pigmentation, textural, and/or contour alterations11. Infection12. Asymmetry13. Temporary injury to nerves (neuropraxia) where nerve branches are superficial

I N M O D E
aesthetic solutions

Clinical Evaluation of Safety and Efficacy of Radio-Frequency Assisted Lipolysis (RFAL) of Breast Envelope and Nipple-Areolar Complex (NAC) Position

Protocol No:
DO607738A

Rev. Date: August, 2018

SIRB ID: 6254

Scope and Duration of the Study

The clinical study will include up to 10 subjects at one site. Eligible subjects will receive single treatment according to the study protocol and will be followed up for a period of up to 1 year to document treatment safety and efficacy.

DEVICE DESCRIPTION

The system is a bipolar RF device where the first RF electrode is the treatment cannula delivering the RF energy to the adipose tissue, vessels, subcutaneous matrix and the subdermal space and the second RF electrode is connected rigidly to the first electrode via a hand piece and is applied to the skin surface above the first electrode. The second electrode creates a transcutaneous pathway for the radiofrequency energy, localizing the electrical energy between the electrodes and eliminating the need to ground the patient. The second electrode is also able to monitor, in real time, the skin surface temperature, allowing for a greater degree of safety while heating the subdermal and subcutaneous tissues.

Sagging, deflated breasts are a complaint of women worldwide following childbirth, weight loss or aging. This problem can be corrected in some women with implant placement, but not all women want larger breasts. Even fewer want the scars associated with traditional mastopexy, especially those women with darker skin types. With 9 out of 10 patients choosing nonsurgical options for aesthetic treatment, a procedure where skin is not excised is deemed preferable by the majority of patients seeking correction of droopy breasts.

Recent studies showing tissue tightening with subsequent skin surface area reduction following treatment with radiofrequency assisted devices indicated a minimally invasive pathway towards treating breast ptosis. Questions regarding this type of treatment include longevity of correction, changes within the breast parenchyma over time and the degree of improvement possible with this minimally invasive technique.¹

	Clinical Evaluation of Safety and Efficacy of Radio-Frequency Assisted Lipolysis (RFAL) of Breast Envelope and Nipple-Areolar Complex (NAC) Position	
	Protocol No: DO607738A SIRB ID: 6254	Rev. Date: August, 2018

The proposed method of RFAL and tissue tightening is based on controlled heating of the fibrous bands attached to the under-surface of the skin as well as the external skin surface and blood and tissue coagulation, leading to skin contraction in treated area. The potential advantages of the RF current treatment are:

- Coagulation of blood vessels which provides for an opportunity for less ecchymosis following the procedure
- Less mechanical damage
- Higher efficacy in fibrous and difficult to treat body contour areas
- Skin tightening

The InModeRF is a Radio-Frequency device comprising of the following main modules:

- AC/DC power supply isolating system modules from AC voltage
- RF generator providing output of RF power to the hand piece
- Microcontroller controlling RF output, monitoring tissue electrical parameters, skin surface temperature and proper functioning of electronic modules.

InModeRF DEVICE

Hand piece delivers RF power to the subject and has the following main elements

- Internal electrode insulated with Teflon with a treatment tip at the distal end
- External electrode with temperature sensor
- Mechanism adjusting distance between electrodes

[figure not shown]
I N M O D E
aesthetic solutions

Clinical Evaluation of Safety and Efficacy of Radio-Frequency Assisted Lipolysis (RFAL) of Breast Envelope and Nipple-Areolar Complex (NAC) Position

Protocol No:
DO607738A

Rev. Date: August, 2018

SIRB ID: 6254

HAND PIECE

Principles of operation

Operation of InModeRF device is based on the concept of a minimally invasive procedure. The hand piece is comprised of two electrodes where an internal electrode is inserted into subcutaneous fat layer and its size is designed for thermal destruction of adipose tissue with RF energy. A second external electrode is applied to the skin surface. Both electrodes have a rigid connection with an adjustable distance between them. RF power and tip size of the internal electrode are designed to liquefy fat in the vicinity of the electrode tip. The external electrode has a much larger area that creates much lower power density on the skin of the patient. The RF current flows from the internal electrode to the external electrode. The hand piece can monitor both tissue impedance and temperature in real time. The outer temperature measurement acts as safety mechanism that stops the RF current in the case the skin temperature is reaches the desire temperature set by the doctor. The figure below shows RF energy distribution in tissue between electrodes.

[figure not shown]
I N M O D E
aesthetic solutions

Clinical Evaluation of Safety and Efficacy of Radio-Frequency Assisted Lipolysis (RFAL) of Breast Envelope and Nipple-Areolar Complex (NAC) Position

Protocol No:
DO607738A

Rev. Date: August, 2018

SIRB ID: 6254

RF energy distribution between electrodes

STUDY DESIGN

Prospective, self-controlled, open label, single arm clinical study

CLINICAL PROCEDURE

At the first visit, the Investigator will discuss with the subject the various treatment alternatives for a Breast Ptosis, both non-surgical and surgical, including the minimally invasive RF and other treatment modalities.

VISIT 1:

SCREENING

During the first visit, the investigator or a representative on his behalf will obtain an Informed Consent Form (ICF) from the subject, clearly indicating his/her understanding of the requirements and risks involved with study participation.

Possible adverse effects include but not limited to bleeding, infection, scarring, skin contour irregularities, thermal trauma to the skin, asymmetry, scarring, surgical shock, pulmonary complications, skin loss, seroma, allergic reaction, and anesthesia related complications can occur and should be discussed and understood. The subject must understand the importance of pre-treatment and

	Clinical Evaluation of Safety and Efficacy of Radio-Frequency Assisted Lipolysis (RFAL) of Breast Envelope and Nipple-Areolar Complex (NAC) Position	
	Protocol No: DO607738A SIRB ID: 6254	Rev. Date: August, 2018

post-treatment instructions and that failure to comply with these instructions may increase the probability of complications.

The Investigator will obtain a focused subject medical history including exclusion criteria specified herein and the front, back and both sides of the treatment area using a high resolution digital camera, as well as additional information that is specified in the case report form.

The follow-up visits should be scheduled 1 week, 6 weeks, 3 months, 6 months and optional 12 months after the treatment.

Photographs should be taken prior to the baseline treatment and at each of the follow-up visits, as well as Vectra 3D Imaging and static measurements. Participants must have a recorded mammogram prior to the first treatment. All measurements will be recorded on the case report form (CRF).

VISIT 2:

TREATMENT

The treatment will be performed once. The treatment procedure should be conducted according to the following guidelines:

INMODE
aesthetic solutions

Clinical Evaluation of Safety and Efficacy of Radio-Frequency Assisted Lipolysis (RFAL) of Breast Envelope and Nipple-Areolar Complex (NAC) Position

Protocol No:
DO607738A

Rev. Date: August, 2018

SIRB ID: 6254

Treatment Parameters

Treatment area	Treatment depth	Hand Piece	External Cut-off Temperature	Internal Cut-off Temperature	Treatment time

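### Does the inclusion bullet leave open whether ptosis is required, and does its augmentation item clash with the implant exclusion?

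*Combined protocol and SAP*

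**What the plan says.** The protocol synopsis, under Main Eligibility Criteria, has a single bullet on the breast condition: "Presence of grade I-III Breast Ptosis, mastopexy with history of breast augmentation, correction of asymmetry, mastopexy alone, mastopexy following implant removal", closing with "modest breast reduction in combination with or without lipoaspiration". That makes six items, one a physical finding and five operations, joined by commas and a final conjunction.

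The exclusion list in the same table bars "Permanent implant in the treated area such as metal plates and screws, silicone implants or an injected chemical substance". It also bars surgery in the treatment area within the past 6 months.

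Elsewhere the protocol describes its target as follows:

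- The synopsis entry on study design speaks of "using Radiofrequency (RF) energy for minimally invasive breast lift procedure".
- The Device Description starts from sagging breasts and presents RFAL as a minimally invasive way to treat ptosis. On implants it says: "This problem can be corrected in some women with implant placement, but not all women want larger breasts".
- Clinical Procedure has the investigator discuss, at the first visit, "various treatment alternatives for a Breast Ptosis, both non-surgical and surgical".
- The Benefits section names nipple-areolar lift.

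The design is "Prospective, self-controlled, open label, single arm clinical study". On size, Scope and Duration says: "The clinical study will include up to 10 subjects at one site".

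**The concern.** The bullet does not say how its items combine, or whether the operations are past events, reasons for seeking treatment, or procedures done alongside RFAL. If any one item is enough, a woman who wants only asymmetry corrected, or a modest reduction, qualifies without ptosis. Efficacy is judged by before/after change in one small arm. A few women with little to lift could therefore pull the average down, and the reported change would no longer describe ptotic breasts.

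The second point is internal consistency. Mastopexy with a history of augmentation is listed apart from mastopexy after implant removal, which suggests that the first item means women whose implants are still in place. The exclusion list bars silicone implants in the treated area, and the treated area is the breast. It is then unclear whom the first item is meant to admit.

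**Working it through.** No design figure can be reproduced. The sample size is stated without effect size, variability, power or error rate. The check is therefore a comparison of texts.

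**1. How the bullet can be read.**

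- *All six items required.* Not workable: a mastopexy on its own cannot sensibly also be one with prior augmentation and one after implant removal.
- *Ptosis required, the rest as context.* Every subject has ptosis.
- *Ptosis required, plus one listed operation or history.* Every subject has ptosis, but the group is narrower.
- *Any one item is enough.* A woman without ptosis could enter.

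Only the last reading raises the concern, and it is narrower than it looks. The Device Description treats mastopexy as a surgical answer to sagging breasts, so the three mastopexy items themselves point to ptosis. That leaves two of the six items, asymmetry and reduction, as possible routes in without it.

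**2. What the rest of the protocol says.** The study design, rationale, first-visit discussion and stated benefit all assume ptosis or lift. No section describes a subject treated for anything else.

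**3. Past, planned or concurrent operations.** The 6-month exclusion limits recent surgery in the area. The Visit 2 instructions describe RFAL through a small access incision, with aspiration, and contain no skin excision. The document does not say what the operations in the bullet mean, but it also gives no sign that another breast operation accompanies or follows treatment.

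**4. The implant item.** A subject must meet the inclusion criteria and none of the exclusions.

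- A woman with silicone implants in the treated area fails the exclusion, whatever the inclusion item says.
- A woman whose implants were removed is not barred by it, and the next mastopexy item already covers her.

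The overlap makes the augmentation item partly redundant. It does not create a rule that gives two answers for the same woman.

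**5. Possible size.** One woman is 1/10 = 10% of a full sample, and more of a smaller one. Going further needs two quantities that the document does not give: *m*, the number of 10 women without ptosis, and *f*, the fraction of the ptotic women's mean lift that they achieve. On those assumptions:

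pooled mean lift ÷ ptotic-only mean lift = 1 − (*m*/10)(1 − *f*)

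- *m* = 1, *f* = 0: 1 − 0.1 × 1 = 0.90
- *m* = 3, *f* = 0: 1 − 0.3 × 1 = 0.70
- *m* = 3, *f* = 0.5: 1 − 0.3 × 0.5 = 0.85
- *m* = 0, or *f* = 1: 1.00

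This is an identity with assumed inputs, and its range includes no effect. It also covers lift only. The objective includes the breast envelope as well as nipple position, and the static measurements include base width, pinch test and skin stretch.

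**6. What is already collected.** Appendix I schedules weight, static measurements, photographs and 3D images at Visit 1 for every subject. The static measurements include the notch-to-nipple and nipple-to-fold distances. Three independent plastic surgeons are to assess preoperative and postoperative photographs. A woman entered without ptosis could be identified from this material.

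**7. Would results by entry item help?** Six items over 10 women average 10/6 ≈ 1.7 women per item if each woman is counted once, and she need not be, because ptosis can coexist with any other item. Such a table would add nothing useful.

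**The case for a change.** The strongest case for a change is that the investigator must decide eligibility from the written criteria, and those criteria do not say that ptosis is required. Context shows what the sponsor probably meant, but context is not a criterion. In a sample this small, one or two women admitted under the looser reading would be a visible share. Clarifying one bullet would cost almost nothing.

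Part of this stands. The bullet is badly drafted, and the augmentation item and the implant exclusion would read better if the sponsor reconciled them. What does not follow is that the plan yields a wrong result. The argument needs the loosest reading, an enrolled woman without ptosis, a smaller gain in that woman, and an analyst who ignores the baseline data. The document establishes none of these.

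Asking for other breast surgery at or after Visit 2 to be recorded and analysed separately goes further still, since the protocol gives no indication that such surgery takes place. The case report form is not among the documents, so it cannot be said to lack these items.

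**Conclusion.** The concern does not call for a change to the plan. The bullet leaves a detail unstated, and the rest of the protocol points one way on it. Applying the criterion already requires the investigator to grade ptosis, and the baseline images and measurements let an analyst see who had it. Each subject is her own control, so a mixed entry group affects whom the average describes and does not unbalance a comparison between arms. Data Analysis promises descriptive statistics and comparison tests where applicable. It states no threshold that a different reading would move. If a woman without ptosis were enrolled, an analyst would naturally report that number and show the before/after results for all women beside those for women with ptosis. With at most 10 subjects this would be descriptive only.

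The implant point is a drafting overlap with no consequence for the analysis, because the exclusion applies on either reading.

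The effect on results is zero if every enrolled woman has ptosis. Otherwise the document gives no means of sizing it. This conclusion assumes that the exclusions are applied as written and that the scheduled Visit 1 assessments are made.

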- A prophylactic antibiotic regimen may be prescribed for subjects starting one day before treatment until one-week post-treatment according to physician discretion. Prophylactic antibiotics should be administered on the day of treatment and continued for a minimum of 2 doses following the RAL procedure.
- Discomfort can be reduced by cool compresses or standard post-operative analgesic.
- Compression garments may be used for up to 6 weeks.
- Appropriate vigorous exercise restrictions should be instituted.
- Subject is to contact physician if there is any indication of infection, fever, excessive swelling, redness, undue pain, shortness of breath, swelling of the ankles, chest pain, irregular heart beat or any other unusual or untoward symptom.

I N M O D E
aesthetic solutions

Clinical Evaluation of Safety and Efficacy of Radio-Frequency Assisted Lipolysis (RFAL) of Breast Envelope and Nipple-Areolar Complex (NAC) Position

Protocol No:
DO607738A

Rev. Date: August, 2018

SIRB ID: 6254

SAFETY AND RESULT MEASUREMENTS

Photography

At each of the specified time points (before the treatment and at the follow-up visits), photos of the body should be taken, including a frontal photo, back photo and two side images of the body from knee up to breast line as it is shown in the picture on the next page. Hands of the subject should be at the side of the body in the position that does not block and does not shade the treated area.

The photos should be taken under controlled conditions, including the colour of the background material, distance from the camera, angle and lighting, including flash, in order to achieve consistent, high-quality before & after pictures. Each picture should be accompanied with the date, visit number, subject ID, subject initials.

Vectra 3D Photography

3D photography of the breast region will be taken in all patients during the routine preoperative work-up using a commercial 3D scanner, VECTRA XR scanner (Canfield Scientific). Patients will be asked to stand with their arms in varying positions and each scanning takes approximately 1–2 seconds. Photographs will be created in both standard format and pixelated format to highlight surface contour.

Weight

Subject weight measurements should be taken before the treatment and at each follow-up visit.

Static Measurements

Additional evaluation of changes in breast shape, including upper pole fullness, breast projection, and bottoming out will be assessed by static measurements:

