- Sternal Notch to Nipple
- Nipple to IMF
- Base Width (at point of breast take off from chest wall)

INMODE
aesthetic solutions

[figure not shown]
Clinical Evaluation of Safety and Efficacy of Radio-Frequency Assisted Lipolysis (RFAL) of Breast Envelope and Nipple-Areolar Complex (NAC) Position

Protocol No:
DO607738A

Rev. Date: August, 2018

SIRB ID: 6254

- Nipple to nipple.

1. Base width (BW)
2. Nipple to inframammary fold distance (N-IMF)
3. Intermammary distance
4. Sternal notch to nipple distance (SN-N)
5. Soft tissue pinch test (PT)
6. Maximum skin stretch (MSS)

EVALUATION

Three independent plastic surgeons will evaluate photographs of the preoperative and postoperative photographs at 3-, 6- and if applicable, 12-month results.

DISCONTINUATION

Subjects enrolled in the study will be free to discontinue their participation in the study at any time. A decision to discontinue participation will not prejudice their medical care. In those instances, Investigators will attempt to obtain clinical results and side effect evaluation concerning the subject prior to his/ her withdrawal.

INMODE
aesthetic solutions

Clinical Evaluation of Safety and Efficacy of Radio-Frequency Assisted Lipolysis (RFAL) of Breast Envelope and Nipple-Areolar Complex (NAC) Position

Protocol No:
DO607738A

Rev. Date: August, 2018

SIRB ID: 6254

DATA ANALYSIS

Statistical analysis of all major body factors will be performed to determine quantitatively the treatment efficacy.

The data will be analysed by the Sponsor using basic descriptive statistics, as well as comparison tests, where applicable. Treatment-related complications will be monitored and reported; if applicable, their incidence rate will be calculated and analysed for any relationship to treatment parameters and/or skin type.

RISK/BENEFIT ANALYSIS

RISKS

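### No masking is described for the Vectra or static measurements, so in this single-arm study a reading shift adds directly to the estimated change in nipple position; a coded, shuffled Vectra read would reduce this cheaply

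*Combined protocol and SAP*

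**What the plan says.** The Study Objectives row of the Protocol Synopsis sets the target as the breast envelope and "Nipple-Areolar Complex (NAC) Position as measured by the Vectra 3D circumferential imaging system". No endpoint is labelled primary. The Study Design section describes a "Prospective, self-controlled, open label, single arm clinical study", and the Synopsis gives the size as "Up to 10 adult subjects".

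Under Clinical Procedure, Visit 1, photographs are taken before treatment and "at each of the follow-up visits, as well as Vectra 3D Imaging and static measurements". The same section adds: "All measurements will be recorded on the case report form (CRF". Appendix I also marks 3D images and static measurements at every visit.

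The Static Measurements section gives the manual distances, which include sternal notch to nipple and nipple to inframammary fold, a secondary role: "Additional evaluation of changes in breast shape, including upper pole fullness, breast projection, and bottoming out will be assessed by static measurements".

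Under Photography, each picture carries its date and visit number. The Evaluation section has three independent surgeons assess pre- and postoperative photographs at 3, 6 and possibly 12 months. It does not say whether they are masked to time point. Under Data Analysis, "The data will be analysed by the Sponsor using basic descriptive statistics", with comparison tests where these apply. No test, significance level or sidedness is given.

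The supplied text is silent on who takes the static measurements, how distances are obtained from the Vectra images, and whether the reader can see earlier values, the visit or the treatment status.

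**The concern.** Every efficacy estimate here is a before-after change in treated women. There is no concurrent group in which the same reading habits would operate and cancel out. If whoever reads the distances knows that an image or a woman is post-treatment, or can see the baseline value, a tendency to read a little more lift goes into the estimate in full. Nothing planned would reveal it.

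The independent surgeons do not close this gap. Their task is to assess photographs, and no distance is mentioned. Even if their photographs were taken to include the 3D images, no masking to visit is described. The quantity named in the objective therefore has no described protection against expectation.

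**Working it through.** **What can be reproduced.** The plan states no power, significance level, SD or effect size, so it has no figure to check. What follows is an illustration.

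**Inputs from the documents.** n = 10 is the ceiling in the Synopsis. The comparison is self-controlled, that is, change from baseline within each woman.

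**Assumptions.** The test is a paired t-test on the change, two-sided at 5%. The true change is zero. The reading shift is *d*, in SDs of the change, and is varied from 0 to 1 because the documents give no value.

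**Formula.** With a shift *d* and no true change, the paired t statistic follows a noncentral t distribution with n − 1 degrees of freedom and noncentrality *d*√n. The chance of a significant result in the favourable direction is P(T > critical value). For n = 10 the critical value is 2.262 (9 degrees of freedom) and √10 = 3.162.

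| Shift *d* (SD of change) | Noncentrality, n = 10 | Favourable significant, n = 10 | Favourable significant, n = 8 |
|---|---|---|---|
| 0 | 0 | 2.5% | 2.5% |
| 0.1 | 0.316 | 4.7% | 4.3% |
| 0.25 | 0.791 | 10.6% | 8.9% |
| 0.5 | 1.581 | 29.3% | 23.1% |
| 0.75 | 2.372 | 56.2% | 44.9% |
| 1.0 | 3.162 | 80.3% | 68.1% |

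The n = 8 column is there because 10 is a maximum. Counting both tails at n = 10 gives 5.0%, 5.9%, 10.9% and 29.3% for *d* = 0, 0.1, 0.25 and 0.5.

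**In centimetres.** A 0.5 cm shift corresponds to a different *d* for each assumed SD of the change. At n = 10 the favourable rate is 80.3% for an SD of 0.5 cm, 29.3% for 1.0 cm, 15.5% for 1.5 cm and 10.6% for 2.0 cm.

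**Without a test.** The 95% confidence interval half-width at n = 10 is 2.262/3.162 = 0.715 SD. A shift of 0.25 SD moves the centre of the interval by 0.25/0.715 = 35% of that half-width, and 0.5 SD moves it by 70%. A purely descriptive report is displaced by the same amount.

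**What masking could recover.** Start from a 0.5 SD shift (29.3%). Removing half leaves 0.25 SD (10.6%), and removing all of it returns 2.5%. The documents do not say what share a coded read would remove.

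**The case against.** **The size is not anchored.** The bias is assumed, and so is the test. At 0.1 SD the favourable rate rises only from 2.5% to 4.7%. In a study of at most 10 women with no confirmatory test, this is an improvement to a measurement process, not a failed inference. This stands, so the figures show sensitivity and are not the trial's error rate.

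**Masking can only be partial.** At a live follow-up visit everyone present knows the woman has been treated, so hiding earlier values limits anchoring and nothing more. Healing access-port incisions, bruising or swelling may identify early images, and with so few women a treating reader may recognise a subject. This also stands. A reader might infer that coding and hidden values fully solve the problem; the documents do not support that.

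**Details a reader might take as given.** It is easy to suppose that distances are read with a tape, that someone places landmarks on the scans, and that successive readings share one form. The supplied text says none of this, and the CRF itself is not available. Separate visit pages may already exist. If Vectra extraction proves fully automated, the concern about that reading weakens. Nor are the static distances the main measure: the objective names Vectra, and the static set is additional. That the change needs no extra personnel also cannot be confirmed, because staffing is not described.

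**A sternal distance as a check.** It is tempting to add a distance that treatment cannot move. A reader who expects the nipple to rise has no reason to misread the sternum, so a flat result would falsely reassure. It would not settle posture either: arm position can move the nipple without altering a sternal distance, and the Vectra section has arms in varying positions.

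**Recoverability.** If the scans are retained, a coded read is still possible after the last visit. That is true, and it is a reason to write it into the plan before anyone has seen results.

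**Conclusion.** The point holds in limited form. The supplied text describes no masking of the Vectra or static measurements, and with one treated group any systematic reading shift adds one for one to the estimated change in nipple-areolar position.

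Under the assumed test, with n = 10 and no true change, shifts of 0.25 and 0.5 SD raise the chance of a favourable significant result from 2.5% to 10.6% and 29.3%. This rests on an assumed bias, an assumed test and the maximum sample size.

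A reader might go further and conclude that the measurements are biased, or that a specific remedy would remove the bias. The documents show neither. They show an unprotected route into the stated objective, which can be narrowed using images the plan already collects.

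**What to change.** 1. Extract all Vectra distances in one batch after the last visit, from images coded and shuffled so that subject, date and visit are hidden.
2. Have the code held by someone other than the reader. Where existing study or sponsor personnel allow, use a reader who did not treat the subject.
3. State in Data Analysis that the efficacy conclusion rests on this read.
4. Take live static readings without sight of earlier values. State that they remain unmasked to visit and treatment and are supportive only.
5. Acknowledge that early images may be partly unmasked by healing, and that the coded read does not correct for changes in weight or arm position.

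**Cost.** No new visits, subjects or procedures are needed. Appendix I gives at most 7 imaging visits per woman, so 10 × 7 = 70 imaging sessions to code and read, plus a coding list and one person to keep it. The main downside is that Vectra results are not available visit by visit.
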